5.1.3 Other study parameters (if applicable)

Other study parameters are muscle strength, activity limitations, self-reported knee joint stability, performance-based activity limitations (GUG, 10-m walk test), co-morbidity, duration of (gait) complaints and radiographic Kellgren/Lawrence score.

A series of demographic variables will be obtained including age, gender, height, weight.

Other study parameters specific to study B are satisfaction and adherence of the gait modification. The change in cognitive demand of the gait modifications between the initial and final training weeks will also be considered in study B.

5.2 Study procedures

The below text describes the individual measurements that will be undertaken during Study A and Study B. For an overview of what will be measured in Study A and at each interval of Study B, see APPENDIX A2.

Gait Real-time Analysis Interactive Lab (GRAIL)

Experiments and training will be conducted on the GRAIL, Gait Real-time Analysis Interactive Lab (MOTEKForceLink), situated in the VR-laboratory of the VU medical centre, rehabilitation department. This high-tech gait lab consists of a virtual reality system for gait biofeedback.

The GRAIL uses a dual-belt instrumented treadmill, an immersive virtual reality environment, an optoelectronic movement recording system with wireless, light-reflecting markers for accurate (<0.5 mm) and easily analysable 3D motion capture (Vicon), electromyography (EMG, ZeroWire), software for system integration and control (D-Flow [83]), and software for real-time musculoskeletal modelling (Human Body Model HBM [43;84]).

The instrumented treadmill has two full 6D force plates underneath each belt. This configuration enables measurement of ground reactions forces under each foot separately

during walking. This is needed as an input to calculate real-time joint kinetics (net joint moments and joint load), kinematics and muscle forces.

The length of the treadmill is 2.20m to accommodate almost unrestricted walking, and to allow for some positional changes of the subject during walking at self-paced walking speed (i.e. the speed of the belt is automatically adjusted to the subject's comfortable walking speed [85]). The GRAIL offers the possibility to obtain many consecutive strides, which can each be measured accurately. Subjects will wear a safety harness during the trials, to protect them in the event of a fall.

Figure 1. Gait Real-time Analysis Interactive Lab, VUmc

Marker placement

Prior to measurement, 42 markers for the reconstruction of the position and orientation the lower limb bones in space (kinematics) will be placed on the subjects. During the measurements, the Human Body Model [84] will be used to calculate real-time kinematics and kinetics that can be used for the real-time feedback.

In the data-analysis post-measurement, anatomical frames according to Cappozzo will be used to calculate the joint kinematics [86;87]. The kinematic data (joint angles) and kinetic data (GRF and knee joint moments) will be time normalized to 100% of the stance phase. The external knee moments will be expressed with respect to the femur anatomical frame and will be normalized to body weight (BW in N) and height (H in meters)(%BW * H). The early stance peak (ESP), midstance (MS) and late stance peak (LSP) will be determined on the basis of the characteristic shape of the vertical component of the GRF vector.

| Segment | Anatomical landmark |
|------------|---------------------|
| Thorax (5) | Navel |

| | Processus Xyphoideus |
|-----------------------------|---|
| | Incisura jugularis |
| | Processus Spinosus Thoracalis 10 |
| | Processus Spinosus Cervical 7 |
| Pelvis (5) | Right Spina Iliaca Anterior Superior |
| | Left Spina Iliaca Anterior Superior |
| | Right Spina Iliaca Posterior Superior |
| | Left Spina Iliaca Posterior Superior |
| | Os Sacrum |
| Thigh (6 on right and left) | Trochanter Major |
| | Lateral side upper leg (at different heights to distinguish left and right leg) |
| | Anterior side upper leg (same height as lateral) |
| | Anterior side upper leg (inferior position) |
| | Epicondylus Lateralis |
| | Epicondylus Medialis |
| Shank (7 on right and left) | Lateral side lower leg (at different heights to distinguish left and right leg) |
| | Anterior side lower leg (same height as lateral) |
| | Anterior side lower leg (inferior position) |
| | Malleolus Lateralis |
| | Malleolus Medialis |
| | Caput Fibulae |
| | Tuberositas Tibia |
| Foot (5 on right and left) | Calcaneus |
| | Phalanx distalis 1 (on top) |
| | Caput Metatarsale 1 |
| | Caput Metatarsale 2 |
| | Caput Metatarsale 5 |
| | |

Protocol real-time feedback

During the experiment, input from the marker data and the GRFs are used in the Human Body Model [84] to calculate in real-time the KAM, the foot progression angle (toe-in/out), medial thrust (from the marker positions on the thigh) and step width.

Prior to measurement, comfortable walking speed will be determined using small increases in the treadmill speed whilst the patient provides feedback on how comfortable they are at that speed. Fixed pace walking is considered to be preferable for the measurements (compared to self-paced mode) due to differences in the kinetic moments caused by changes in speed. .

| Condition | Description | Time (minutes) | Purpose | Recording time (seconds) |
|-----------|--------------------|----------------|----------------------|-----------------------------|
| 0 | Acclimatization to | 3 (max) | To determine the | 0 |
| | treadmill | | average (mean) speed | |
| | | | of walking of the | |

The following protocol will be used in Study A:

| Condition | Description Time (minutes) Purpose | | Purpose | Recording time |
|-----------|---|--|--|--|
| | | | | (seconds) |
| | | | patient for use in further trials. | |
| 1 | Baseline condition- own shoes | 2 | 30 seconds familiarization plus 90 seconds recording time | 90 |
| 2 | Baseline condition- standard shoes | 2 | 30 seconds familiarization plus 90 seconds recording time | 90 |
| 3i | Implicit learning phase- standard shoes with real time visual feedback on KAM | 2 | 30 seconds familiarization plus 90 seconds recording | 90 |
| 3ii | Implicit learning phase- standard shoes with real time audio feedback on KAM | 2 | 30 seconds familiarization plus 90 seconds recording | 90 |
| | | | | |
| 4 | Training phase with explicit instructions | 3 x 2 mins | Feedback on up to 3 kinematic parameters separately 30 seconds familiarisation plus 90 seconds recording | 270 |
| 5 | Measurement- new pattern with feedback | 2 | Measurement of pattern with direct KAM feedback (30 seconds familiarization and 90 seconds recording) | 90 |
| 6 | Measurement- new pattern | 2 | Measurement of pattern without any feedback (30 seconds familiarization and 90 seconds recording) | 90 |
| | | Total walking time: 19.0 minutes maximum (N.B. Regular breaks can be taken as necessary to prevent fatigue). | | Total recording time: 720 seconds =12.0 minutes in 8 individual recordings. |

In stage 3 of the assessment, the subject will be instructed to decrease the KAM. The subjects will therefore apply an individual kinematic strategy to reach this goal [8;43]. Feedback will provide the subject with knowledge of result but not knowledge of performance

so it will up to the individual to devise their own strategy. At this stage no further instructions will be given about kinematic strategies or compensations. This will allow measurement of the implicit motor learning using an external focus of attention [58].

In step 4, explicit verbal instructions will be given on the gait pattern in addition to the realtime visual KAM feedback to further develop a pattern that can be sustained in daily life (e.g. toe-in/out <15deg). Hunt and Takacs (2014) mentioned that a toe-out position of \pm >15 (difference from baseline) is difficult to obtain [3]. Reference values of step width and medial thrust/ frontal plane position of the knee, will be obtained from the baseline trial and the initial trials with feedback on the KAM. This will enable threshold limits to be set such that the step width (for example) is not increased to an excessive degree. The values of all of the kinematic and kinetics will be available for the researcher in real time. In this way, the instructions to the patient can be adapted to suit the individual patient, based on objective information. In step 6, the optimal gait pattern will maintained by the subject without any feedback.

| Condition | Description | Time | Purpose | Recording |
|-----------|--|---|--|-----------|
| | | | | time |
| | | | | (seconds) |
| 0 | Acclimatization to treadmill | Up to 4 minutes | To determine the average (mean) speed of walking for use in training period | 0 |
| 1 | Baseline condition- own shoes | 60 seconds minutes | 15 seconds familiarization plus45 seconds recording time | 45 |
| 2 | Training phase | Up to 21 minutes depending on the week | This will be based on the results of study A. Explicit guidance will be given as required. Frequency of the feedback will be adjusted if necessary to avoid dependence on it and encourage motor learning. | 0 |
| 3 | Measurement without feedback while new pattern is applied | 60 seconds | 15 seconds familiarization plus 45 seconds recording time | 45 |
| 4i* | Measurement without feedback, -with dual tasking (Stroop test/ memory test) | 75 seconds | 30 seconds familiarization plus 45 seconds recording | 45 |
| | • | | | |

The following protocol will be used in Study B for each of the two sub-groups.:

| 5 | Advice for home | ~8 minutes | Clinician/ physio to offer advice | 0 |
|---|-----------------|------------|-----------------------------------|---|
| | training | | for home training | |

Steps 0,1,2,3 and 5 repeated at weekly intervals.

* Steps 4i, 4ii and 5 will only be applied during week 4 to 6, thus the time taken for training sessions 1 to 3 will be shorter.

Note, the patient can take a break at any time during the training/ assessment The total walking time will depend on the week number; see also Figure 2, which presents the faded feedback approach that will be used. The total duration of the training sessions will be increased during the course of the intervention, with a decrease in the feedback time. This approach (termed faded feedback) has been shown to improve motor learning {Winstein, 1990 265 /id} and has been implemented successfully in several studies related to biofeedback for gait retraining including Barrios et al. (2010), Hunt and Takacs (2014) and Shull et al. (2013).

Figure 2: Progression of training and feedback time during the study

In step five, the researcher will provide the patient with home training advice based on the gait retraining methods used in the preceding stages. This may include advice on how to stand up from a chair or how to ascend/ descend stairs. It is important the home training advice complements the advice provided during the gait re-training session.

In addition to the weekly sessions described above, further measurements will be obtained 3 and 6 months after the last training session. This final measurement will consist of both a baseline measurement and replication of the learned pattern, with and without the cognitive dual tasking.

Real-time visual feedback will be provided on the semi-cylindrical screen of the GRAIL. Various types of feedback are available: e.g. bar plot, polar plot, colour change, graph [43] or a number of the actual peak value. Figure 3 shows some examples of feedback that have been used previously in gait modification protocols on the GRAIL. However, other types of visual feedback, such as footsteps indicating desired foot progression angle and/ or step width have been proposed for this study, and have been given a favourable opinion by clinicians. Audio feedback will also be evaluated in Study A.

Figure 3: Examples of different types of real-time visual feedback that can be used on the GRAIL [43].

Knee pain

Knee pain (study A and B) over the past week will be assessed by an 11 point numeric rating scale (NRS; 0 -10), with higher scores representing more pain. Patients will be asked: "What was your pain rating on average over the past week?"

Knee pain will also be assessed during walking at the different gait modification conditions by an NRS scale. Prior to walking, patients will be asked "What is your pain rating at the moment?". Patients will also be asked about pain during walking: "What was your pain rating on average during walking?" to determine if there is immediate pain relief. To account for the effect of analgesics, patients will be asked if they have taken any pain-killers in the two hours prior to the gait training session.

Muscle activity (EMG)

EMG data will be collected from the following muscles (study A and B, weeks 1, 6 and 3 and 6 months follow up): medial and lateral vastus muscle, medial and lateral hamstrings, medial

and lateral gastrocnemius and rectus femoris. EMG electrodes will be placed conform the EMG guideline protocol (Seniam) in use at our movement labs.

Satisfaction

Satisfaction with the learned gait pattern in study A ("how satisfied are you with the modified gait pattern?" and "how likely are you to continue using this technique after leaving here?") and study B ("how satisfied have you been during the last week with your modified gait pattern since leaving the VUmc where you were assessed?") will be measured. Responses will be required on a 6-point Likert scale, ranging from "completely dissatisfied" to "completely satisfied".

Adherence

Adherence of applying the modified gait pattern during the last week in the training period (study B) will be evaluated through use of a questionnaire, aiming to score the duration, as well as the duration as percentage of total walking time. Patients will be provided with a weekly diary to mark down the duration of time spent using the new walking pattern and their total walking time on a daily basis. It is hoped that in this way, the tendency to over-estimate the duration when asked by a clinician will be avoided. The diary will also include spaces for any side effects, like fatigue, back or knee pain etc. to be reported.

Muscle strength

Muscle strength will be assessed in study A and at the beginning and end of the training period and at 3 and 6 months follow up in study B, specifically for the knee flexors and extensors using an isokinetic dynamometer (Humac Norm, CSMi, Boston, USA). Quadriceps and hamstrings strength are measured isokinetically at 60⁰/second. All patients will be assessed according to a previously described device and protocol [88]. The mean in Nm per kg body weight (Nm/kg) for quadriceps and hamstrings strength of the right and left maximum voluntary contraction obtained from three measurements will be used for analysis.

Self-reported stability

Knee instability will be measured in study A by questioning the perception of knee stability [89] and by questioning the perception of knee confidence during walking [90]. Self-reported knee instability has been defined as the sensation of an episode of buckling, shifting or giving way of the knee in the previous three months [89]. Persons reporting knee instability will be additionally asked for the number of episodes of instability, whether these episodes concerned the left, right or both knees, if any episodes had resulted in a fall, and the

particular activity that induced an episode of instability [26]. Also the amount of falls related to the perception of knee instability will be assessed.

Activity limitations

A self-report questionnaire will be used to assess limitations in daily activities (study A and at the beginning and end of the training phase in study B and at the 3 and 6 months follow us): the Western Ontario and MacMasters Universities Osteoarthritis Index (WOMAC) [91;92]. The Dutch version of the WOMAC will be used [93]. The WOMAC is a disease specific measure of pain, stiffness, and physical function for individuals with OA of the knee. The WOMAC, with a possible range of 0-96, includes 5 items related to pain, 2 items related to stiffness, and 17 items related to physical function (PF). Each item is scored on a 5-point Likert scale. Reliability and validity of the WOMAC have been established [93]. Higher scores on the WOMAC represent greater reduction in functional ability. The ICC for Dutch WOMAC physical-functioning is 0.92 [93].

Performance-based activity limitations

Performance based activity limitations will be assessed in study A and at the 3 and 6 months follow up in study B with both two standardized physical performance tests (GUG, and 10-meter walk test, respectively). As a performance-based measure of function a get up and go (GUG) test [94;95], and a 10m-walk test [96], all timed with a stopwatch, will be used. The GUG test is conducted over a distance of 15 m, comparable to Hurley et al. [94]. The intra class correlation coefficient (ICC) for the intra-tester reliability of the GUG test is 0.98 and the ICC for the inter-tester reliability is 0.98 [95]. The 10m-walk test is a test assessing the time to walk a distance of 10 m along a level and unobstructed corridor. Patients will be instructed to walk as fast as possible and timed with a stopwatch.

Radiography

Radiographs of the knee are scored in a blinded fashion by an experienced radiologist using the grading scales proposed by Kellgren & Lawrence (KL) [73-75]. Weight-bearing, anteroposterior radiographs of the knee joints are obtained following the Buckland-Wright protocol [97].

Patients recruited directly through the VUmc and not through the AMS-OA cohort will be requested to have a radiograph of their knee(s) at the VUmc to confirm or refute the presence of osteoarthritis primarily in the medial compartment.

Demographics

A series of demographic variables will be obtained including age, gender, height, weight, and duration of (gait) complaints.

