the various gait modification conditions (study A: 1. baseline; 2. KAM feedback without kinematic instructions, audio and visual feedback; 3. Kinematic feedback without further instructions (toe-out or -in, step width and medial thrust); 4. KAM feedback with additional verbal kinematic instructions about an effective gait pattern that can be sustained in daily life: 5. maintaining the pattern from 4. without any feedback) and during and after the training sessions (study B: 1. baseline; 2. try to replicate the pattern learned in study A without feedback; 3. KAM feedback with kinematic instructions from study A; 4. maintaining the pattern from 3. without feedback; follow-up after 3 and 6 months). Linear mixed models will be used to calculate statistical differences. Secondary parameters will include external knee flexion moment (KFM), and kinematic pattern (joint angles and temporal-spatial parameters) as measured by the GRAIL; pain as measured by the numeric rating scale and will be assessed during the different gait modification patterns (as for the KAM).

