2. OBJECTIVES

The primary objective of study A is:

• To evaluate the use of real-time visual and audio feedback on the knee adduction moment during gait in patients with knee osteoarthritis to decrease the biomechanical load on the knee via implicit learning and explicit instructions.

The secondary objective of study A is:

- To evaluate changes in the kinematic patterns and electromyographic patterns between baseline (without feedback) and modified (with feedback) gait patterns.
- To identify factors based on the demographic, radiographic and baseline kinematics which increase the likelihood in reducing the KAM using the biofeedback training method.

The primary objectives of study B are:

- To provide proof-of-concept for the use of real-time feedback as a clinical intervention on gait retraining to decrease the biomechanical load on the knee in patients with knee osteoarthritis during a 6 weeks training and 3 and 6 months follow-up.
- To assess changes in pain and function as a result of the biofeedback gait training programme; this will be measured using the WOMAC questionnaire and NRS pain scale. Pain and function are important outcome measures for the patient and are therefore included as additional primary outcome measures.

The secondary objective of study B is:

i) To estimate the reduction in cognitive demand (and hence the extent of motor learning) of the gait modifications over the six week retraining period.

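### Study A lists visual before audio KAM feedback with no counterbalancing, describes its kinematic/explicit step in three ways, and prints totals that do not match its rows

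*Protocol*

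**What the plan says.** **Order of the feedback modes.** Section 5.2 introduces the table with "The following protocol will be used in Study A" and then numbers the conditions: 0 acclimatisation; 1 and 2 baselines; 3i, "Implicit learning phase- standard shoes with real time visual feedback on KAM"; 3ii, "Implicit learning phase- standard shoes with real time audio feedback on KAM"; 4 training with explicit instructions; 5 the new pattern with feedback; 6 the new pattern without feedback. No random or balanced order of conditions is given anywhere. The only random step in the protocol is the choice of patients for Study B when more than 30 qualify (section 4.1).

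**What the comparison is for.** The primary objective of Study A (section 2) begins "To evaluate the use of real-time visual and audio feedback on the knee adduction moment during gait" and covers both implicit learning and explicit instruction. Section 5.2 adds that audio feedback is to be evaluated in Study A, and the Study B table says its training phase will rest on the Study A results.

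**The kinematic/explicit step.**
- Summary, condition 3: "3. Kinematic feedback without further instructions (toe-out or -in, step width and medial thrust".
- Section 5.2 table, condition 4: a training phase with explicit instructions, with "Feedback on up to 3 kinematic parameters separately".
- Section 5.2 text: "In step 4, explicit verbal instructions will be given on the gait pattern in addition to the realtime visual KAM feedback".

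**Totals.** The table ends with a maximum walking time of 19.0 minutes and "Total recording time: 720 seconds =12.0 minutes in 8 individual recordings".

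**The concern.** Conditions 3i and 3ii set the same task, lowering the KAM, and differ only in how the signal is presented. The protocol treats this phase as motor learning, so practice in the first trial can be expected to carry into the second, and fatigue can act in the opposite direction. If audio comes second for everyone, a difference between the modes cannot be separated from a difference between first and second attempts. At stake are the evaluation of the two modes that the objective calls for and whatever Study B takes from it.

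The kinematic/explicit step raises a separate problem. The Introduction asks whether the advantage of direct KAM feedback over kinematic feedback, seen in healthy subjects, also holds in patients. That can be answered only if it is fixed whether KAM is on display in this step. The descriptions disagree on this, and also on whether instructions are given.

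The totals matter because they leave open whether each patient performs both implicit trials at all.

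**Working it through.** **1. The plan's own sample size.** Inputs from section 4.4: effect size 0.45, two-sided alpha 0.05, power 0.80, paired t-test. With noncentrality d·√n and n − 1 degrees of freedom, n = 41 gives 0.45 × √41 = 2.88 on 40 df, and power 0.803. The stated 41 is reproduced. It refers to KAM with versus without feedback, not visual versus audio.

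**2. Table totals.** Rows of the Study A table in section 5.2:

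| Condition | Walking (min) | Recording (s) | Recordings |
|---|---|---|---|
| 0 | 3 | 0 | 0 |
| 1 | 2 | 90 | 1 |
| 2 | 2 | 90 | 1 |
| 3i | 2 | 90 | 1 |
| 3ii | 2 | 90 | 1 |
| 4 | 3 × 2 = 6 | 270 | 3 |
| 5 | 2 | 90 | 1 |
| 6 | 2 | 90 | 1 |
| **Sum** | **21** | **810 (13.5 min)** | **9** |
| Printed | 19 | 720 (12.0 min) | 8 |

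Removing one two-minute, 90-second trial gives 21 − 2 = 19 min, 810 − 90 = 720 s and 9 − 1 = 8 recordings, which match all three printed figures. Appendix A2 has a single row for implicit learning, and the Summary lists audio and visual feedback together as one condition. Both are consistent with one implicit trial, but neither settles the matter.

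**3. The kinematic/explicit step, side by side.**

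| Source | Instructions? | Signal fed back |
|---|---|---|
| Summary, condition 3 | No | Kinematic |
| 5.2 table, condition 4 | Yes | Kinematic, up to three parameters one at a time |
| 5.2 text, step 4 | Yes | Visual KAM |

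The numbering differs between sources. The Summary's own condition 4 (KAM feedback with verbal instructions) agrees with the text's step 4. The conflict is one of content: the Summary's kinematic step and the table's condition 4 show a kinematic signal, while the text attaches KAM feedback to step 4. In the table, KAM feedback after the implicit phase returns only at condition 5.

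**4. Illustration of an order effect.** The documents give no size for a practice or fatigue effect, so the values here are assumptions. With a fixed order, no true difference between modes and n = 41, a shift of δ (in SD of the paired difference) gives noncentrality δ√41. The chance of two-sided p < 0.05 is then:

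| δ (assumed) | δ√41 | Chance of a spurious difference |
|---|---|---|
| 0 | 0 | 5.0% |
| 0.1 | 0.64 | 9.6% |
| 0.2 | 1.28 | 24.0% |
| 0.3 | 1.92 | 46.6% |
| 0.4 | 2.56 | 70.5% |

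**5. Cost of balancing.** A two-sequence design with a period term leaves n − 2 = 39 df. At d = 0.45 and n = 41, power is 0.802, against 0.803 without the period term. No extra patients are needed.

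**The case against.** The strongest reply is that no visual-versus-audio test is planned. Section 7.1 compares baseline with the gait modification conditions, section 4.4 powers KAM with and without feedback, and both the objective and the Summary name the two modes together. This stands. A reader might infer that the protocol's primary analysis carries a false-positive rate of 24% to 70%; the documents do not support that. Those rates describe a direct comparison that section 7.1 does not name, under order effects that were assumed.

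Nor does any sentence declare the order of 3i and 3ii fixed. The order is read from one numbered sequence and from the absence of any balancing. The fair criticism is that the protocol specifies a sequence without balancing it.

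A reader might also infer that Study B's feedback mode is chosen by a rule from Study A. The text says only that Study B training is based on Study A results. The choices it does describe are individual: the Appendix A1 decision tree, and each patient's KAM reduction and satisfaction under section 4.2.

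The placing of implicit before explicit cannot be faulted, because Appendix A1 uses implicit-phase measurements to choose the instructions. Randomising the kinematic trials within condition 4 would serve no planned contrast, since they are up to three parameters selected per patient. Even on the text's reading, condition 4 does not simply duplicate condition 5: the first is a three-trial training phase, the second a single measurement of the resulting pattern.

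None of this answers the mismatch between rows and totals, the conflicting descriptions of the step, or the lack of balance between two modes that the objective sets out to evaluate.

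**Conclusion.** The point holds in limited form.

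- **Order.** As written, any visual-audio comparison is confounded with practice or fatigue. The harm falls on the evaluation of the two modes and on its use for Study B training, not on the primary baseline contrasts. Its size is unknown.
- **Content of the step.** Three descriptions differ on instructions and on the displayed signal, so it is unclear whether the KAM-versus-kinematic question in the Introduction can be answered. The documents do not show which description was intended.
- **Totals.** The rows exceed the printed totals by 90 s, one recording and 2 min. Either one implicit trial is not done by every patient or the totals are wrong; the documents do not say which.

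The change is worth making because it is nearly free and the comparison it protects belongs to the Study A objective.

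**What to change.** 1. State whether every patient performs both 3i and 3ii, and make the rows, the totals and Appendix A2 agree. If both are done, the totals are 810 s (13.5 min), 9 recordings and 21 min.
2. If both are done, randomise their order (about 20 and 21 patients per sequence) and include trial order in the mixed model. If they are not both done by everyone, state who does which and on what basis.
3. Reconcile the Summary, the table and the text of section 5.2 to one definition of the kinematic/explicit step, stating whether instructions are given and which signal is displayed. Use one numbering of conditions throughout.
4. Keep implicit before explicit, and report that contrast as including the effect of practice.

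Cost: a short randomisation list, one degree of freedom, slightly more set-up between trials, and protocol wording. No trials are added to those already listed, and no patients.
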